## Methods and Material

### Study design

To address the aim of the study, an open-label, randomised controlled trial (RCT) will be conducted, as well as a qualitative interview.

Participants will be allocated in a 1:1:1 ratio to either: treatment as usual by a general practitioner (TAU-GP), treatment as usual by a psychologist (TAU-P) in the form of cognitive

behavioural therapy (CBT), or an algorithm-based medical treatment by a general practitioner (ALGO). The duration of the study is up to 14 weeks, with 12 weeks of treatment and up to 2 weeks between screening and baseline. Participants will be evaluated at baseline, 4 weeks, 8 weeks and 12 weeks after baseline, respectively. For all 3 arms, an external rater will carry out the Hamilton Depression Rating Scale (HAM-D) screening.

The study design and duration are illustrated in Figure 1.

[figure not shown]

Figure 1: Study Design (GP: General practitioner. TAU: Treatment as usual. PSE: Present State Examination).

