### Inclusion criteria

1. The participant must be referred to the study with a diagnosis of unipolar depressive disorder, as judge by the GP.
2. Severity of the depressive episode corresponding to moderate depression, as judged by the GP.
3. Clinical uncertainty regarding which of the treatments, medication or psychotherapy, would be the better choice in the case concerned.
4. Age criteria: Participants must be at least 18 years old and no more than 65 years old at the time of randomisation.

5. The participant must be a patient in general practice.
6. Participants must be able to participate in virtual meetings (e.g. by phone or computer) and have e-Boks.
7. The participant must be willing to receive psychotherapy by a psychologist and/or medication.
8. Must have signed the document of informed consent.

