## Statistics and Power Calculation

### Statistics

The difference in HAM-D6 score between baseline and follow up will be compared between the three groups. A F-test will be used to assess if there is a significant difference among the groups. The analysis will be applied to the mITT population using last-observation-carried-forward (LOCF).

The three different treatment groups will be directly compared to each other, i.e. TAU-GP against ALGO, TAU-GP against TAU-P and TAU-P against ALGO. The groups will be compared based on the change in HAM-D6 scores from baseline to endpoint using a two-sided t-test (difference-in-differences [DID] analysis), along with other relevant secondary outcomes.

The DID-analysis will be applied to the mITT population at 12 weeks using LOCF, and the PP12 population.

In secondary analysis, differences between treatment groups regarding changes during the study period for each of the HAM-D6, MDI, PSP, C-SSRS, and Brief INSPIRE-O scores, will be analysed in separate mixed effects models. The models will be analysed with the relevant outcome as dependent variable, and time, treatment, and their interaction as fixed effects as well as patient and centre as random effects, also using the mITT and PP12 populations.

The proportion of responders (defined as a 50% reduction of HAM-D6 score) or remitters (defined as a HAM-D6 score  $\leq 5$ ) will be compared between the three groups, using chi-square tests for association and/or Poisson regression with a robust estimation of the standard error. The same will be applied to the remaining categorical variables. The analyses will be performed by using the mITT population. A similar analysis will be carried out for the categorical variable reasons for treatment discontinuation in the ITT population.

Further, risk of adverse events and serious adverse events is compared by applying Poisson regression with a robust estimation of the standard error in the mITT population.

To investigate the differences in time to all-cause discontinuation and duration of sick leave after baseline between the three groups, compared two and two, the time in the study will be compared by applying a two-sided t-test. Analysis of sick leave days is carried out on the mITT population and time to all-cause discontinuation will be performed on the ITT population.

Concordance between HAM-D6 and MDI will be analysed visually.

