Exploratory analyses will extend the primary linear mixed-effects model by adding baseline variables (age, sex, educational level, baseline HAM-D6, duration of untreated depression, age at first episode, psychiatric/physical comorbidity, prior treatment history and DART score). If deemed feasible, non-linear dynamics as the interaction with treatment arm or an estimation using splines will be included. Relevant effects will be reported as regression coefficients or odds ratios with 95 % CIs and visualised in stratified plots where relevant.

All model assumptions are checked visually and sensitivity analyses, using bootstrap to estimate standard errors, are conducted in case of any violations.

All secondary outcomes will be analysed regardless of the significance of the primary outcome.

The statistical analyses will be performed by a statistician at the Department of Psychiatric Research, Aalborg University Hospital, Psychiatry, using Stata 19.

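### The secondary mixed models are specified with patient and centre random effects only, so their standard errors for week 0 to 12 arm contrasts may be wrong, and are typically too small if correlation falls with time between visits

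*Protocol*

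**What the plan says.** All references are to the protocol.

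- **Visits** (Study design): "Participants will be evaluated at baseline, 4 weeks, 8 weeks and 12 weeks after baseline, respectively". Each scale in these models is therefore measured four times.
- **Secondary mixed models** (Statistics): "In secondary analysis, differences between treatment groups regarding changes during the study period" are analysed in a separate model for each of HAM-D6, MDI, PSP, C-SSRS and Brief INSPIRE-O, with "time, treatment, and their interaction as fixed effects as well as patient and centre as random effects". The section names no random slope, residual covariance or robust variance for these models, and does not say whether time is categorical or linear. For the Poisson models, the same section does name a robust standard error.
- **Primary test** (Statistics): "A F-test will be used to assess if there is a significant difference among the groups", applied to HAM-D6 change.
- **Pairwise comparisons** (Statistics): based on "change in HAM-D6 scores from baseline to endpoint using a two-sided t-test".
- **Safeguard** (Statistics): "All model assumptions are checked visually and sensitivity analyses, using bootstrap to estimate standard errors, are conducted in case of any violations".
- **Scale** (Power calculation): the SD of the week 0 to 12 HAM-D6 change is taken as 3.9 in every arm. No SD at a single visit and no correlation between visits is given.

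**The concern.** A random intercept for patient and another for centre, with nothing else stated, imply compound symmetry: equal variance at every visit and the same correlation between any two visits. The model then estimates one residual variance by pooling all six pairs of visits and uses it for every contrast. The week 0 to 12 change uses the pair furthest apart. In repeated symptom ratings, correlation commonly falls as the interval grows. That change then varies more than the model allows, and its standard error comes out too small.

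At stake are the confidence intervals and p-values of five secondary models, and of the exploratory predictor analyses that extend them. On the mITT population, these models are also the only planned HAM-D6 score analyses that could use all observed visits without carrying values forward or restricting to completers. Their standard errors should therefore be dependable.

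**Working it through.** **The plan's own figures.** With three groups, SD 3.9, alpha 0.05 and one arm 2.25 points from the other two, the F-test noncentrality at 45 per arm is 45 × (2/3) × 2.25² / 3.9² = 9.98. The power is 0.805, so 45 reproduces. 45 / 0.8 = 56.25, so 57 reproduces. Nothing below bears on that calculation.

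**Inputs.** From the protocol: four visits, SD of change 3.9, 57 per arm. Assumed: visit SDs and correlations, each set rescaled so that the SD of change is 3.9. Complete data are also assumed. Patient and centre intercepts then cancel out of a change score.

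**Formulas**, for a 4 × 4 visit covariance matrix:

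1. Residual variance the random-intercept model settles on: s² = mean variance − mean covariance.
2. Variance of week 0 to 12 change under the model: 2s².
3. True variance of that change: V0 + V12 − 2·Cov(0,12).
4. SE ratio r = √(model variance / true variance). It depends on neither scale nor sample size.
5. Type I error of a nominal 5% two-sided test: 2Φ(−1.96 r).

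**Example A: equal SDs, correlation 0.7 / 0.49 / 0.343 at 4 / 8 / 12 weeks** (unit variance).
- Mean covariance = (3 × 0.7 + 2 × 0.49 + 0.343) / 6 = 0.5705, so s² = 0.4295.
- Model variance 0.859; true variance 2 × (1 − 0.343) = 1.314.
- r = √(0.859 / 1.314) = 0.81, and type I error = 2Φ(−1.585) = 11.3%.
- The true SE with 57 per arm is 3.9 × √(2/57) = 0.731. The model reports 0.731 × 0.8085 = 0.591.

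**Example B: SDs 2.5, 4, 4, 4, constant correlation 0.5.**
- Mean variance = (6.25 + 3 × 16) / 4 = 13.5625. Mean covariance = 0.5 × (3 × 10 + 3 × 16) / 6 = 6.5. So s² = 7.0625.
- Model variance 14.125; true variance 6.25 + 16 − 2 × 0.5 × 10 = 12.25.
- r = 1.07, and type I error = 3.5%. The SE is too large.

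**Range across assumed patterns** (week 0 to 12 contrast, categorical time):

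| Correlation | Visit SDs | SE ratio | Type I error |
|---|---|---|---|
| Constant 0.5 | Equal | 1.00 | 5.0% |
| AR(1) 0.5 | Equal | 0.86 | 9.2% |
| AR(1) 0.7 | Equal | 0.81 | 11.3% |
| AR(1) 0.8 | Equal | 0.79 | 12.4% |
| 0.60 / 0.45 / 0.30 by lag | 2.5, 3, 3.5, 4 | 0.83 | 10.3% |
| 0.50 / 0.40 / 0.30 by lag | 2.5, 3, 3.5, 4 | 0.88 | 8.4% |
| AR(1) 0.7 | 2.5, 3.5, 4, 4.3 | 0.83 | 10.5% |
| AR(1) 0.7 | 2.5, 4.2, 4, 3.2 | 0.998 | 5.0% |
| Constant 0.5 | 2.5, 3, 3.5, 4 | 0.96 | 6.0% |
| Constant 0.5 | 2.5, 3.5, 4, 4.3 | 0.996 | 5.1% |
| Constant 0.5 | 2.5, 4, 4, 4 | 1.07 | 3.5% |
| Constant 0.5 | 4, 4.2, 4.2, 3 | 1.09 | 3.3% |
| Constant 0.5 | 2.5, 4.2, 4, 3.2 | 1.24 | 1.5% |

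A still sharper peak in spread (2.5, 4.2, 4.2, 2.8, constant 0.5) gives 1.36 and 0.8%.

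**Linear time.** The slope contrast fares worse under falling correlation: 11.3%, 13.7% and 14.9% for AR(1) 0.5, 0.7 and 0.8 with equal SDs, and 11.8% for the 0.60 / 0.45 / 0.30 pattern.

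**Other contrasts.** The week 0 to 4 contrast errs the other way. For AR(1) 0.5, 0.7 and 0.8 with equal SDs, its SE ratios are 1.14, 1.20 and 1.23.

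**The case against.** The best defence is that the protocol names the random effects but does not say that residuals are independent or of equal variance. A residual structure could be added in a statistical analysis plan without contradicting it, and such detail is often left there. This stands in part. The random part of the model is nevertheless stated, and an analyst who follows the text fits compound symmetry.

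Three further points have weight:

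- **Direction.** A reader might infer that the standard errors are certain to be too small, because entry is limited by "Severity of the depressive episode corresponding to moderate depression, as judged by the GP" and spread must then widen. The documents do not support this. The criterion is the GP's judgement with no HAM-D6 threshold, and no visit SDs are given. The table shows that widening spread at constant correlation does little, or makes the SE too large. Falling correlation drives the inflation, and even that can be offset by an early peak in spread.
- **Safeguard.** The planned visual checks and bootstrap are aimed at this kind of failure. They help only partly: the bootstrap is a sensitivity analysis, the headline intervals stay model-based, and resampling by patient is not stated.
- **Reach.** The week 12 comparisons on each scale already have change-score t-tests that are free of this problem, and the protocol does not say that a week 12 contrast will be read from the mixed models. This stands, and it limits the consequence.

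**Conclusion.** The point holds for the secondary mixed models and the exploratory models that extend them. As written, they impose one variance and one correlation across weeks 0 to 12.

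The size rests on assumed covariances, complete data and, except where stated, categorical time. If correlation falls with lag, the SE of the week 0 to 12 arm contrast is typically about 12-21% too small, with type I error of about 8-12%. With constant correlation, type I error is about 1.5-6%, and the SE ranges from slightly too small to too large. The protocol cannot settle which applies.

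A reader might also infer that the primary result is at risk, because the exploratory paragraph of the Statistics section calls the mixed model primary. That is loose wording. The primary analysis is the F-test on change, and neither it nor the pairwise t-tests use this covariance. The change is worth making before data are seen, but it does not touch the primary conclusion.

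**What to change.** In the mixed-model paragraph of Statistics, specify:

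1. Time as categorical visits, with an unstructured within-patient covariance (4 visits: 4 variances + 6 covariances = 10 parameters) and centre kept as a random effect.
2. REML, with Kenward-Roger or Satterthwaite degrees of freedom.
3. If that model does not converge, a robust variance clustered on patient, or bootstrap standard errors that resample patients, as the reported analysis and not only as a sensitivity analysis.

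The same specification should carry over to the exploratory models. The cost is a change of wording and a few more covariance parameters. If compound symmetry does hold, the loss at 171 patients is negligible. The benefit is that the standard errors no longer depend on an assumption for which the protocol gives no figures, and that the covariance is not chosen after the data are seen.

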## Measures and Outcomes

### Modified intention-to-treat (mITT) population and Per Protocol (PP) populations

The modified intention-to-Treat (mITT) population encompasses all randomised participants with at least one post-baseline HAM-D6 rating. The endpoint of the study is 12 weeks.

For participants with premature endpoints, the latest endpoint available will be used with last-observation-carried-forward (LOCF).

The Per Protocol (PP) populations are defined as completers at week 4 (PP4), at week 8 (PP8), or at week 12 (PP12).

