### Secondary outcomes

All secondary outcomes are based on the mITT population unless otherwise specified. The following secondary outcomes will be explored:

- The difference in differences (DID) in HAM-D6 score, from baseline to end of study, between participants in:
  1. TAU-GP and ALGO
  2. TAU-GP-and TAU-P
  3. TAU-P and ALGO
- The DID in C-SSRS score, from baseline to end of study, between participants in:
  1. TAU-GP and ALGO
  2. TAU-GP-and TAU-P
  3. TAU-P and ALGO
- The DID in MDI score, from baseline to end of study, between participants in:
  1. TAU-GP and ALGO
  2. TAU-GP-and TAU-P
  3. TAU-P and ALGO
- The DID in PSP score, from baseline to end of study, between participants in:
  1. TAU-GP and ALGO
  2. TAU-GP-and TAU-P
  3. TAU-P and ALGO
- The impact of the assigned treatment pathway from the participant's point of view and the participant's personal experience of recovery through a self-rating scale (Brief INSPIRE-O). This will also be done using the DID, from baseline to end of study, between participants in:
  1. TAU-GP and ALGO

2. TAU-GP-and TAU-P

3. TAU-P and ALGO

- The concordance between MDI and HAM-D6.
- Duration of sick leave after baseline (indicated in days) within the current depressive episode.
- A Per Protocol analysis at week 12 (PP12) will also be completed for all continuous secondary outcomes.
- A Per Protocol analysis at week 12 (PP12) will also be completed for the primary outcome.
- Between-group difference for adverse events and serious adverse events.
- Between-group difference for the ITT population in reasons for premature discontinuation, time to all-cause discontinuation

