#### [Discontinuation criteria](#)

- Suicidality according to C-SSRS with a positive score to question 4 or 5 or upon the investigator's discretion.
- Severe somatic illness, as judged by the investigator.
- The patient wishes to stop participation and/or withdraws consent.
- The patient is unable to follow the treatment in one of the arms.
- Treatment will be terminated if the subject does not show up for two virtual meetings with the study staff or two meetings with the GP/psychologist, without cancelling, and

the study personnel are unable to get in contact with the participant. Attempts of contact are documented in the CRF.

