### [Withdrawal and dropout](#)

Withdrawal from the study will occur at the time when any of the discontinuation criterion are fulfilled, as judged by the investigator.

If possible, data regarding all outcome measures will be collected immediately or as soon as possible after the time of withdrawal. The primary outcome measure (HAM-D6) will have the highest priority. The primary reason for discontinuation will be recorded as well as the time of discontinuation. Subjects who have withdrawn will not be replaced.

If a study participant wishes to dropout, an interview regarding the reasons for dropping out will be offered to the patient concerned. The planned next rating session will be executed as soon as possible hereafter.

It is recommended that study participants discuss further treatment with the treating general practitioner responsible for their care.

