## Flowchart of Participant's Course

## Table of Measurements

Week	-2 to -1 Screening	0 Baseline	4	8	12 End of Study	Un-scheduled visit
Meeting form	In person	Virtual meeting	Virtual meeting	Virtual meeting	Virtual meeting	Virtual meeting
Signed Consent Form	X					
Inclusion and exclusion criteria	X					
Oral + written information	X					
Randomisation	X					
Adverse events		X	X	X	X	X
Demographic data	X					
Rating Scales						
HAM-D6		X	X	X	X	X
C-SSRS	X	X	X	X	X	X
PSP		X	X	X	X	
DART		X				
PSE						X*
Self-report forms						
MDI		X	X	X	X	
Brief INSPIRE-O		X	X	X	X	

HAM-D6: The Hamilton Depression Scale, item 6.

C-SSRS: The Columbia-Suicide Severity Rating Scale.

PSE: Present State Examination.

MDI: Major Depression Inventory.

PSP: The Personal and Social Performance Scale.

DART: The Danish Adult Reading Test.

\*In person

All visits and phone calls are scheduled within the defined time frame +/- 3 days. Pre-screening is conducted by a phone call by the investigator or study staff. The written study information will be sent in advance of the screening visit, and if the patient prefers, the letter of consent will also be sent prior to screening. The screening visit is a physical meeting where oral and written information is presented, and written consent can be obtained. Should the patient wish to, they can have at least 24 hours and no more than a week to consider the consent form. A follow-up meeting will be scheduled.

If, during the screening visit, the patient is found to meet all criteria for trial participation, the first treatment visit (baseline visit) will be scheduled within 14 days of the screening. The patient is randomised to treatment at screening.

A virtual baseline meeting is scheduled with the investigator or a competent research assistant. Study visits (virtual meetings) at 4, 8 and 12 weeks, as well as potential telephone calls, are scheduled with the investigator or study staff. Both screening and baseline visits are study related.

Table 1 further visualises the duration of time of each rating scale and interview as well as type of the rating scale, along with the duration of time and type for the different kinds of visits.

	Duration	Type
C-SSRS	1. visit 20 minutes (hereafter 5 minutes)	Rating scale - Interview
PSP	15 minutes	Rating scale - Interview
DART	5 minutes	Rating scale - Interview
HAM-D6	15 minutes	Rating scale - Interview
PSE	60-90 minutes	Semi-structured interview

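### AE and SAE risk is compared only in patients with a post-baseline HAM-D6, and no dated SAE check to week 12 is set for patients withdrawn early

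*Protocol*

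**What the plan says.** **Outcome and analysis.** Protocol, Secondary outcomes, lists "Between-group difference for adverse events and serious adverse events". Under Statistics, "risk of adverse events and serious adverse events is compared by applying Poisson regression with a robust estimation of the standard error", and the same sentence assigns this to the mITT population. No risk window is stated. The same section uses the ITT population for reasons for, and time to, discontinuation.

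**Analysis set.** The mITT population is "all randomised participants with at least one post-baseline HAM-D6 rating". Randomisation comes before baseline: "The patient is randomised to treatment at screening" (Table of Measurements), and baseline follows within 14 days.

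**Leaving the study.** "Withdrawal from the study will occur at the time when any of the discontinuation criterion are fulfilled, as judged by the investigator". The criteria include "Suicidality according to C-SSRS with a positive score to question 4 or 5 or upon the investigator's discretion", severe somatic illness, and "The patient wishes to stop participation and/or withdraws consent". After that, "If possible, data regarding all outcome measures will be collected immediately or as soon as possible after the time of withdrawal", with HAM-D6 given first priority. For a patient who drops out, the next planned rating is brought forward.

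**Collection of events.** The Table of Measurements marks adverse events at baseline, weeks 4, 8 and 12, and unscheduled visits.

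**Records.** Under Information from Patient Medical Record, a hospital record (EPJ) is created for each participant. Consent covers use in the study of treatment information, including adverse events and inpatient and outpatient contacts, and staff have access for the whole trial period. General practice records are not directly accessible.

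**The concern.** There are two gaps.

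The first is the analysis set. Membership of the safety comparison depends on an efficacy rating. A patient randomised at screening who has an SAE and leaves before a post-baseline HAM-D6 is excluded, even when the study knows of the event. The protocol fixes this set, so it is not a detail left open for the analysis plan.

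The second is follow-up after exit. Meeting a discontinuation criterion ends study participation, not only treatment. A patient withdrawn for suicidality at week 4 or week 8 has a rating from that visit and so counts in the mITT denominator. That patient then has 56 or 28 of the 84 days with no scheduled check. Some of these patients leave because their risk is raised. An analysis plan can adjust for observed time, but adjustment alone does not supply events that nobody looked up.

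At stake is the completeness of a listed secondary safety outcome in which few events are expected.

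**Working it through.** **Inputs from the protocol.** 171 patients, 57 per arm, 20% dropout, 12 weeks (84 days). The planned size reproduces: 45 / 0.80 = 56.25, rounded up to 57, and 3 × 57 = 171. The protocol gives no figure for the AE/SAE comparison.

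**Assumptions, not in the protocol.** Leaving times are uniform over the 84 days. The 12-week SAE risk r is 2%, 5% or 10%, with constant hazard that does not change at exit. Dropout by arm is varied below.

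**1. Patient-time after exit.** Leavers: 0.20 × 171 = 34.2. Mean time left: 42 days. Time after exit: 34.2 × 42 = 1,436 of 171 × 84 = 14,364 days, or 10.0%. With other leaving patterns the share is 6.7% (spread over weeks 4 to 12: 0.20 × 1/3) to 13.3% (all just after week 4: 0.20 × 2/3).

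**2. How much lies outside mITT.** One extreme is that no leaver before week 4 has a rating:
- before week 4: 11.4 leavers × 70 days = 798 days, outside mITT;
- from week 4 on: 22.8 leavers × 28 days = 638 days, inside mITT, which is 638 / (159.6 × 84 = 13,406) = 4.8% of mITT time;
- share outside: 798 / 1,436 = 56%.

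The other extreme is that every leaver gives an exit rating. Then all are in mITT and the share outside is near 0. The protocol aims for the second case but promises it only if possible.

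**3. Expected first SAEs after exit, whole trial.** With H = −ln(1 − r), the mean chance per leaver of a first SAE after exit is r/H − (1 − r). For leavers from week 4 on it is [exp(−H/3) − exp(−H)] / (2H/3) − (1 − r).

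| r | H | all 34.2 leavers | 22.8 leavers from week 4 |
|---|---|---|---|
| 2% | 0.0202 | 34.2 × 0.00997 = 0.34 | 0.15 |
| 5% | 0.0513 | 34.2 × 0.0248 = 0.85 | 0.37 |
| 10% | 0.1054 | 34.2 × 0.0491 = 1.68 | 0.74 |

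If half the leavers already have a counted SAE at exit (assumption), the values halve: 0.42 and 0.19 at 5%. If the hazard triples after exit (assumption), the approximate number missed per arm is 57 × r × 3 × 0.20 × 0.5 = 0.34, 0.86 or 1.71.

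**4. Between-arm effect.** Take true ratio 1.00, unchanged hazard, and dropout of 15% v 25% (assumption).
- All leavers in the denominator: (1 − 0.25/2) / (1 − 0.15/2) = 0.875 / 0.925 = 0.946.
- Leavers before week 4 excluded: s(p) = [(1 − p) + (2p/3)(2/3)] / (1 − p/3), so s(0.25) / s(0.15) = 0.939 / 0.965 = 0.974.

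At 20% in both arms and equal later rates the ratio stays 1.00.

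**5. Sampling error for comparison.** At r = 5% and 57 per arm: exp(±1.96 × √(2 × 0.95 / (57 × 0.05))) = 0.20 to 4.95. Power to separate 5% from 10% is about 17%.

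**The case against.** A reader might infer that the protocol plans no SAE ascertainment at all after exit, so that later events have no route into the analysis. The documents do not support that. The medical-record section provides for adverse-event and hospital-contact information to be used in the study. It gives staff access throughout the trial and does not end either at withdrawal. What is missing is narrower: a date, a systematic rule for withdrawn patients, and a link to the SAE outcome. The section's stated reason for using the information is mainly the treatment plan, with project execution and oversight given for access. A permission of this kind does not ensure the same look-up for every leaver in an open-label trial.

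A reader might also take the 56% outside mITT as the expected figure. It is the upper end. The exit HAM-D6 has first priority, and a patient who gives one enters mITT.

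Third, one might infer a materially biased safety comparison. With equal withdrawal and equal later rates there is no bias, and the illustrated 15% v 25% shift is far inside sampling error. The comparison is largely descriptive.

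It can fairly be said that a dated record check could be written into another trial document before database lock, since the hospital record persists. That stands for the check. It does not stand for the analysis set, which the protocol states outright. Nor is every patient affected: the event that leads to exit is seen and may already count, and the ITT comparison of discontinuation will show unequal follow-up.

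**Conclusion.** The point holds as a modest improvement in safety reporting. Tying the AE/SAE comparison to a post-baseline HAM-D6 can exclude randomised patients with known serious events. Early leavers, including those withdrawn for suicidality, have no dated or systematic SAE check up to week 12.

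The size is small: about 10% of patient-days, and about 0.3 to 1.7 first SAEs in the whole trial under an unchanged hazard, more if risk rises after exit. Only the trial size, the 12 weeks and the 20% dropout come from the protocol. SAE risks, leaving times, hazard after exit and dropout by arm are assumptions. The primary result and the sample size do not depend on this point.

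**What to change.** **Statistics.** Analyse AEs and SAEs in all randomised patients, the ITT set already used there for discontinuation, and keep the robust Poisson risk model.

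**Withdrawal and dropout.** State that SAEs, including suicidal acts and hospital admissions, are counted to 12 weeks after baseline, or after the planned baseline date if that visit did not take place. For each patient withdrawn early who has not withdrawn consent to data use, existing staff check the EPJ once at the week-12 date, whether or not there is a post-baseline HAM-D6. Patients who withdraw consent to data use contribute events known up to that date, and their number per arm is reported.

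**Cost.** A sentence or two in each section and at most about 34 record checks (about 17 if half the leavers withdraw consent to data use, an assumption).

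**Limits.** Only SAEs visible in the hospital record are recovered. Leavers and stayers are then ascertained differently, which the report should say. Events seen only in general practice, and non-serious AEs after exit, stay uncounted.

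### Adverse events are compared only in participants with a post-baseline HAM-D6 rating, so a known event in an unrated early leaver is dropped

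*Protocol*

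**What the plan says.** The Statistics section fixes the population for the safety comparison, for AEs of any kind as well as for SAEs, as follows: "serious adverse events is compared by applying Poisson regression with a robust estimation of the standard error in the mITT population". The section on analysis populations says that this set "encompasses all randomised participants with at least one post-baseline HAM-D6 rating". The Secondary outcomes section lists the between-group difference in AEs and SAEs without naming another set, under the general rule "All secondary outcomes are based on the mITT population unless otherwise specified". The Protocol defines no safety population.

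Discontinuation is treated differently. The Statistics section analyses "reasons for treatment discontinuation in the ITT population", and does the same for time to discontinuation.

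Three provisions bear on who ends up without a rating:

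- Withdrawal and dropout: "If possible, data regarding all outcome measures will be collected immediately or as soon as possible after the time of withdrawal", and "The primary outcome measure (HAM-D6) will have the highest priority". For a participant who wishes to drop out, the next planned rating session is brought forward.
- Table of Measurements: HAM-D6 and adverse events are both collected at weeks 4, 8 and 12 and at unscheduled visits. AE recording starts at baseline, but "The patient is randomised to treatment at screening", and baseline may follow up to 14 days later.
- Two sources can reveal an event without a rating. Under Withdrawal and dropout, "The primary reason for discontinuation will be recorded as well as the time of discontinuation". Under Information from Patient Medical Record, record information on adverse events and on hospital and outpatient contacts is used in the study.

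**The concern.** Entry to the safety comparison depends on an efficacy rating made after randomisation, and the event being counted can itself stop that rating from happening. Someone who is hospitalised, refuses further contact or cannot be reached before any rating is removed from the AE and SAE analysis even when the study team knows what happened. The same person appears in the ITT discontinuation analysis as having left, with a reason, but not as a participant with an AE or SAE.

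Serious events are most exposed. They are few, so losing one or two changes the reported risk visibly, and they can be learned from hospital records without a study visit. If unrated leavers have more events than rated participants, risk is understated within the arm. Bias between arms would arise only if such losses differed by arm, which the Protocol gives no evidence of.

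**Working it through.** **Inputs from the Protocol.** 57 participants per arm, 171 in total, and 20% expected dropout (Power calculation; Study population). The plan's inflation reproduces: 45/(1 − 0.20) = 56.25, rounded up to 57, and 3 × 57 = 171. None of these figures changes under this point.

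**Which participants are affected.** Expected dropouts per arm are 57 × 0.20 = 11.4. The Protocol does not say how many leave before any post-baseline HAM-D6, so unrated leavers per arm lie between 0 and 11.4. The upper end would need every dropout to go unrated, which the withdrawal provisions are meant to prevent. It is a bound, not an expectation.

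**Formulas.** For one arm, let *u* be the number of unrated leavers, *a* the rated participants with an event and *b* the unrated leavers with a known event.

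- Risk in mITT = *a* / (57 − *u*)
- Risk in all randomised = (*a* + *b*) / 57

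mITT understates the risk when *b*/*u* exceeds *a*/(57 − *u*).

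**SAEs** (*a* = 1; all counts are assumptions):

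| *u* | *b* | mITT | All randomised |
|---|---|---|---|
| 1 | 1 | 1/56 = 1.8% | 2/57 = 3.5% |
| 3 | 2 | 1/54 = 1.9% | 3/57 = 5.3% |
| 3 | 0 | 1/54 = 1.9% | 1/57 = 1.8% |

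The third row shows that the choice of set hardly matters when unrated leavers have no SAEs.

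**Any AE.** Assume 50% risk among 54 rated participants and *u* = 3 with AE risk *p*. Risk in all randomised is (0.5 × 54 + 3*p*)/57, which is 47.4%, 50.0% or 52.6% for *p* = 0, 0.5 or 1, against 50% in mITT. The shift is at most 2.6 percentage points either way.

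**Effect on a test.** Against a comparator arm with 1/57, the two-sided Fisher exact p-value is 0.62 for 3/57 and 1.0 for 1/54. Neither is near significance, so what changes is the reported risk.

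**The case against.** The strongest reply is that AEs and HAM-D6 are collected at the same visits. Every scheduled or unscheduled post-baseline visit that records AEs also records HAM-D6, so the mITT set is close to the set in which AEs are actually ascertained. This largely stands for ordinary AEs: a person with no later rating will often have had no later AE interview either.

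A second reply is that the record route is limited. The Protocol says that general-practice records are not directly open to study staff, and it sets out no systematic AE search for people who have left. That weakens the route for events managed in general practice. It does not remove it for hospital-recorded SAEs.

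Third, early exits for suicidality or severe somatic illness are discontinuation reasons and so are compared by arm in the ITT set. That is partial cover, because those exits are not reported there as AEs or SAEs.

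Fourth, the remedy has a weakness of its own. Counting unassessed leavers as event-free dilutes AE risk: with a true risk of 50%, 3 such leavers give 0.5 × 54/57 = 47.4%, as large a shift as the AE error illustrated. This stands as a reason to report how many were not assessed. It does not justify discarding events that are known.

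Finally, ITT is named in the Protocol but never defined, so a corrected sentence must describe the population and not rely on the label.

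**Conclusion.** The concern holds. Followed as written, the Protocol excludes known events in participants who have no post-baseline HAM-D6 rating. This is a stated choice of population, not a detail left open for a later analysis plan.

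Its reach is modest. It concerns SAEs mainly, one secondary comparison, and probably few participants. It does not touch the primary analysis or the sample size. In the assumed examples, an arm's SAE risk would be reported as 1.8% or 1.9% when the known events support 3.5% or 5.3%. With no events among unrated leavers there is no material effect. These figures rest on assumed counts, because the Protocol gives neither an event rate nor the share of dropouts who leave unrated. Differential loss between arms is possible but not shown. It is a cheap improvement and worth making.

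**What to change.** In the Statistics section, state that AEs and SAEs are compared in all randomised participants, irrespective of any HAM-D6 rating, and that events known from any source count. An acceptable alternative is all randomised participants who attended the baseline visit. The Table of Measurements section treats that visit as the start of treatment, AE recording begins there, and this set leaves out people lost in the up to 14 days between randomisation and baseline. Choose one and describe it in full.

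List it under Secondary outcomes as an exception to the mITT default. Keep the planned Poisson regression with robust standard errors. Report, by arm, how many participants had no AE assessment after baseline.

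The cost is one changed sentence and one exception, with no new data collection. Two drawbacks should be acknowledged: ordinary AE risk may be slightly diluted by leavers who were never assessed, which the reported count makes visible, and the all-randomised set includes people who never started their allocated pathway.
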